## 2. SYNOPSIS

Name of sponsor/company: Aptinyx Inc.	
Name of investigational product: NYX-783	
Name of active ingredient: [REDACTED]	
Title of study: A Study to Evaluate the Safety and Efficacy of NYX-783 in Subjects with Post-Traumatic Stress Disorder	
Study center: Multicenter (up to approximately 30 enrolling sites)	
Studied period (years): Estimated date first subject enrolled (screened): January 2019 Estimated date last subject enrolled: June 2020	Phase of development: 2

Study Objective: The overarching goal of this exploratory study is to investigate the safety and tolerability of NYX-783 in a PTSD population, and to characterize the response profile of PTSD symptoms to NYX-783 treatment, as assessed by the intrusion, avoidance, and negative alterations in cognition and mood, and arousal & reactivity subscores as well as the total score on the Clinician-Administered PTSD Scale for the Diagnostic and Statistical Manual of Mental Disorders, 5th edition (CAPS-5)
 
Primary Objective:
 
 
To assess the effects of NYX-783 compared to placebo on reducing the severity of Post-Traumatic Stress Disorder (PTSD) symptoms as measured by the Clinician-Administered PTSD Scale for the Diagnostic and Statistical Manual of Mental Disorders, 5th edition (CAPS-5).
 
 
Secondary Objectives:
 
 
To assess the effect of NYX-783 compared to placebo in the following outcomes: a) change in symptoms of PTSD as measured by the PTSD-Checklist for DSM-5 (PCL-5), b) change in sleep quality as measured by the Pittsburgh Sleep Quality Index (PSQI) Global Score and the PSQI Addendum for PTSD (PSQI-A) Global Score and the PSQI Addendum for PTSD (PSQI-A) Global Score, and c) change in cognitive function as measured by the Symbol Coding from the Brief Assessment of Cognition (BAC Symbol Coding).
 
To assess the effect of NYX-783 compared to placebo in the change in global clinical severity of PTSD symptoms as measured by the Clinical Global Impressions-Severity (CGI-S) scale.
 
To compare NYX-783 vs. placebo in the change in levels of anxiety and depression as measured by the Hospital Anxiety and Depression Scale (HADS).
 
To assess the safety and tolerability of NYX-783 compared to placebo.
 
 
Exploratory Objectives
 
 
[REDACTED]
 
	

- [REDACTED]
- [REDACTED]
- [REDACTED]
- [REDACTED]
- [REDACTED]
- [REDACTED]
- [REDACTED]
- [REDACTED]

**Methodology:**

Study Design

This is a Phase 2, multicenter, randomized, double-blind, placebo-controlled, parallel-group, outpatient study using a sequential parallel comparison design (SCPD). The study will consist of 3 periods: Screening, Treatment, and Follow-up. The Treatment period will be conducted in 2 stages to examine the efficacy and safety of NYX-783 compared to placebo in the treatment of PTSD symptoms. Randomization in Stage 1 (Weeks 1-4) will be 4:1:1 (placebo: NYX-783 50 mg QD: NYX-783 10 mg QD, respectively *treatment arms [1], [2] and [3]*). In Stage 2, both placebo responders and non-responders (CAPS-5 total score reduction from baseline [Day 1]  $\leq 35\%$  and CAPS-5 total score  $\geq 26$  at Week 4) from Stage 1 will be re-randomized (in a stratified manner) in a blinded fashion in a 3:2:2 ratio (placebo: NYX-783 50 mg QD: NYX-783 10 mg QD) (*treatment arms [4],[5],[6] and [7],[8],[9]*, respectively). All subjects who received active NYX-783 in Stage 1 will receive placebo in Stage 2 (*treatment arms [10] and [11]*), which will provide information about the duration of effects of NYX-783 as taken during Stage 1, while taking placebo during Stage 2.

**Screening period:**

Written informed consent must be provided by potential study participants prior to the initiation of any protocol-specified procedures. Subject eligibility will be confirmed in a 2-step process: 1) Screening Visit (Days -28 to -14): Subjects will be screened for PTSD using the PCL-5, with the Life Events Checklist for DSM-5 (LEC-5) being used to assess the nature of the primary traumatic event. The primary eligibility criteria will be confirmed by the investigative site using the Structured Interview for DSM-5® (SCID-5-CT), and the within the past month version of the CAPS-5. Additional eligibility assessments will include demographics, medical history, vital signs, physical examination (PE), height, weight, electrocardiogram (ECG), laboratory samples, suicidality, and concomitant medication information. Other clinical measures will be used to assess sleep quality, cognitive effects, as well as mood and anxiety symptoms. 2) SAFER interview (Day -14  $\pm 3$  days): Eligible subjects with a primary diagnosis of PTSD, a PCL-5  $\geq 38$ , and a CAPS-5 total score  $\geq 30$  as assessed by the investigative site, will participate in a SAFER remote phone interview to confirm the

diagnosis of PTSD and evaluate related primary exclusion criteria. Subjects who meet the eligibility criteria during the SAFER interview will be qualified to proceed to the Day 1 randomization visit.

**Treatment Period:**

On Day 1, severity of PTSD symptoms will be assessed by the investigative site using the CAPS-5 and PCL-5. Other clinical measures will be used to assess sleep quality, cognitive effects, as well as mood and anxiety symptoms. Assessments will also include vital signs, ECG, weight, laboratory samples, and concomitant medication information. Eligible subjects will be randomized to receive NYX-783 50 mg QD, NYX-783 10 mg QD, or matching placebo. Study drug will be administered at the investigative site on Day 1 and dispensed for subsequent outpatient administration.

Subjects will return to the clinic for study visits at Weeks 2, 4, 6, and 8/early termination (or conduct remote assessments at Week 2 and Week 6). On these days, PTSD severity will be assessed by CAPS-5 and PCL-5 at the investigative site. Other clinical measures will be used to assess sleep quality, cognitive effects, as well as mood and anxiety symptoms. Additional safety assessments will also be completed. Blood samples for plasma concentrations of NYX-783 will be collected at Week 4 and Week 8/early termination. Blood samples for optional pharmacogenomic testing will be collected on Day 1. Optional blood samples for biomarker (RNA) testing will be collected on Days 1 and Weeks 4 and 8/early termination.

**Follow-up Period:**

A safety follow-up visit will be completed approximately 7 days after the last dose of study drug is administered.

Safety throughout the entire study will be assessed by adverse events, vital signs, weight, physical examination, ECGs, clinical laboratory values, and the Sheehan Suicidality Tracking Scale (S-STs).

Rater qualification, training, and surveillance will be centrally monitored during the study.

A Data and Safety Monitoring Board will periodically review available safety data to determine if it is safe to proceed.

**Number of subjects (planned):** Approximately 156 subjects

**Main criteria for inclusion:**

Inclusion Criteria

1. Male and female subjects between the ages of 18 to 65 years (inclusive) at the time of signing the informed consent.
2. A primary diagnosis of PTSD (DSM-5 criteria, APA, 2013) according to the CAPS-5 and SCID-5-CT, with the primary traumatic event occurring  $\geq 12$  months prior to screening. NOTE: In cases of “delayed-onset PTSD”, clinically manifest PTSD symptoms must be present for at least 6 months prior to screening.
3. PCL-5  $\geq 38$  at screening.
4. CAPS-5 score total score  $\geq 30$  at screening.
5. Qualified to participate according to the SAFER interview.
6. Female subjects of childbearing potential must have a negative serum pregnancy test at screening and be practicing an adequate method of birth control (e.g., oral or parenteral contraceptives, intrauterine device, barrier, abstinence). Subjects may not be breastfeeding or plan to become pregnant or donate ova during the study and for 30 days after the last dose of study drug.
7. Male subjects who are sexually active with female partner(s) must agree to the following during the study and for 30 days after the last dose of study drug: a) use an acceptable method of birth control (condom with spermicide or surgical sterilization) and b) refrain from sexual activity

with female partners who do not use an acceptable method of birth control. Barrier contraception (condom with spermicide) **must** be used by all male subjects who are not surgically sterilized at least 90 days prior to screening. Male subjects must also agree to refrain from sperm donation during the study and until 30 days after the last dose of study drug.

8. Ability to understand the requirements of the study, provide written informed consent, abide by the study restrictions, and agree to return for the required assessments.
9. Willing to use a smartphone-based video recording technology for monitoring compliance with study drug administration.
10. The subject has a stable social situation in the investigator's opinion, e.g. during the course of the study no changes are expected in work, marital, or accommodation status.

#### Exclusion Criteria

1. Complex PTSD, defined as a condition that may develop following exposure to an event or series of events of an extreme and prolonged or repetitive nature of which the subject experienced as extremely threatening or horrific and from which escape was difficult or impossible (e.g., torture, slavery, genocide campaigns, prolonged domestic violence, repeated childhood sexual or physical abuse). If affect dysregulation and interpersonal dysfunction are primary over other core PTSD symptoms, in the investigator's opinion, they should be considered as exclusionary criteria. NOTE: Non-interpersonal trauma (e.g. motor vehicle accident, mass transportation accident, domestic fire, mass shooting survivor) prior to 18 years of age are not exclusionary, and, the trauma can be considered the primary traumatic event (index trauma).
2. Trauma focused psychotherapies including, prolonged exposure therapy, cognitive behavioral therapy, eye movement desensitization and reprocessing (EMDR) within 30 days prior to screening or during the study.
3. Primary traumatic event occurred prior to 2001.
4. Primary traumatic event was followed by further major traumatic life episodes in the 6 months prior to screening.
5. Primary traumatic event was associated with traumatic brain injury (TBI) categorized as Moderate-to-Severe TBI, according to the Mayo TBI Severity Classification System. ([Malec 2007](#)) (see Appendix A).
6. Substance use disorder within the 6 months prior to screening. Use of any illicit drugs of abuse during the study period is prohibited.
7. History of alcohol abuse within the 6 months prior to screening. NOTE: Up to an average of 1 drink/day is allowed during the study.
8. Positive screen for alcohol or drugs of abuse, including phencyclidine, barbiturates, benzodiazepines, opiates, methadone, cocaine, cannabinoids, and amphetamines at screening or Day 1. Subjects who have a positive screen for cannabinoids or other medically prescribed drugs of abuse at screening, must have a negative screen at Day 1 and agree not to use during the study.
9. Any history of schizophrenia or other psychotic disorder, bipolar disorder, psychosis, or other Axis 1 disorder (except for major depressive disorder or anxiety disorders that followed exposure to the trauma, or an anxiety disorder showed a worsening after trauma). NOTE: Anxiety disorders (such as selective mutism, specific phobia, social anxiety disorder, panic disorder, agoraphobia, and generalized anxiety disorder) are exclusionary only if the diagnosis preceded the primary traumatic event, and, the subject was seeking and received treatment for the symptoms prior to the primary traumatic event. A current secondary diagnosis of major depressive disorder without full remission is not exclusionary; if treated, the dose of a permitted

- antidepressant must be stable for at least 30 days prior to screening and expected to continue during the study.
10. Clozapine use or electroconvulsive therapy within 12 months prior to screening or during the study.
  11. Current use of medications with primarily central nervous system (CNS) activity (e.g., antipsychotics, anticonvulsant drugs [including gabapentinoids], psychostimulants, benzodiazepines, methylphenidate, doxazosin, prazosin, clonidine, first-generation sedating H1 antihistamines eszopiclone, zolpidem extended-release or any other sedative-hypnotic medications within 3 days prior to screening or during the study. **NOTE:** Use of certain non-benzodiazepine sleep inducers (e.g., zolpidem immediate-release [up to 10 mg at bedtime], zaleplon [up to 20 mg at bedtime]), melatonin, or ramelteon for sleep are allowed.
  12. Use of nefazodone, selective serotonin reuptake inhibitors (SSRIs, such as fluoxetine, sertraline, escitalopram, citalopram, paroxetine), serotonin and norepinephrine reuptake inhibitors (SNRI-s, such as desvenlafaxine, duloxetine, venlafaxine), reversible and non-reversible monoamine oxidase inhibitors (such as selegiline, phenelzine, tranylcypromine), tricyclic antidepressants (such as amitriptyline, imipramine, nortriptyline), noradrenergic and specific serotonergic antidepressant (NaSSA) mirtazapine, serotonin modulator and stimulator antidepressants such as vilazodone or vortioxetine, or the norepinephrine, serotonin and dopamine reuptake inhibitor bupropion within 30 days (90 days for fluoxetine) prior to screening or during the study. **NOTE:** Subjects on stable treatment ( $\geq 30$  days prior to screening) with St. John's Wort may continue this therapy during the study with no expected change in dose.
  13. Treatment with an injectable depot neuroleptic within 90 days prior to screening or during the study.
  14. Subjects who meet the criteria for suicidal intent, plan and/or behavior on the S-STS at screening or Day 1. These criteria are a score of 3 or 4 on questions 2 or 13, or 2 or higher on any of the following questions: 1a (only if 1b is coded YES), 3, 4, 5, 6, 7, 8, 9, 10, 11, 12, or 14. (**NOTE:** calculation of S-STS total score is not required)
  15. In the process of litigating for compensation for a psychiatric disorder. Subjects who are in the process of applying for medical or VA benefits and/or those who have a settled claim prior to their enrollment in the trial are eligible.
  16. History of Huntington's, Parkinson's, and/or Alzheimer's disease, multiple sclerosis, seizures (history of childhood febrile seizures are not exclusionary), epilepsy, or stroke.
  17. History of allergy, sensitivity, or intolerance to *N*-methyl-D-aspartate receptor (NMDAR) ligands, including ketamine, dextromethorphan, memantine, methadone, dextropropoxyphene, or ketobemidone, as well as current use of such agents.
  18. Received an investigational drug product or device within 30 days (or 5 half-lives, whichever is longer for a drug product) of dosing.
  19. Previously received NYX-783.
  20. Screening QT interval corrected for heart rate (HR) by Fridericia's formula (QTcF)  $>450$  (males) or  $470$  (females) milliseconds (msec) or an ECG that is not suitable for QT measurements (e.g., poorly defined termination of T-wave in the investigator's opinion).
  21. A known familial history or known presence of long QT syndrome, or a known history of past or current clinically significant arrhythmias or ischemic heart disease.
  22. Body mass index  $>35$  kg/m^2 at screening.
  23. HR  $\leq 45$  or  $>95$  beats per minute at screening.
  24. Uncontrolled Type I or Type II diabetes mellitus or uncontrolled hypertension.



25. Estimated creatinine clearance <60 mL/minute (calculated by the Cockcroft-Gault equation) at screening or history of renal disease, as assessed by the investigator or the sponsor-designated medical monitor.

26. Known diagnosis of a current infectious disease, including human immunodeficiency virus infection, hepatitis, or other ongoing infectious disease that the investigator considers clinically significant.

27. Current evidence of dysplasia or history of malignancy (including lymphoma and leukemia) in the last 5 years, except for successfully treated non-metastatic basal cell or squamous cell carcinoma of the skin or localized carcinoma in situ of the cervix.

28. History of gastrointestinal disease or surgery (except simple appendectomy or hernia repair), leading to impaired drug absorption.

29. Known abnormal laboratory results, ECG results, medical history or concurrent conditions which, in the opinion of the investigator or sponsor, would preclude safe study participation or interfere with study procedures/assessments.

30. Uncorrected hypothyroidism or hyperthyroidism. NOTE: Subjects with compensated hypothyroidism with normal thyroid-stimulating hormone levels may be enrolled.

31. Impaired hepatic function characterized by a previous known diagnosis of chronic liver disease and/or the presence of direct bilirubin >1.5x, or, alanine transaminase, aspartate transaminase, alkaline phosphatase, or gamma-glutamyl transferase >2x the upper limit of normal at screening.

32. Current borderline personality disorder, antisocial personality disorder, or other personality disorder (e.g. subject showed pervasive pattern of disregard for and violation of the rights of others, or subject has had previous repetitive suicidal behavior [including aborted, interrupted or ineffective suicide attempts, gestures], self-mutilating behavior, or has ever been homicidal) of sufficient severity, in the investigator's opinion, to interfere with study participation.

33. Use of NMDAR-binding drugs (e.g., ketamine, dextromethorphan, memantine, methadone, lamotrigine, esketamine) within 60 days prior to dosing or during the study.

34. 3,4-Methylenedioxymetamphetamine (MDMA)-assisted psychotherapy within 90 days prior to screening or during the study.

35. Expected to initiate any psychotherapy during the study.


Investigational product, dosage and mode of administration: NYX-783 50-mg oral capsule(s) or matching placebo There are 3 treatment arms:
 

• NYX-783 50 mg QD

• NYX-783 10 mg QD

• Placebo QD

Participant Duration: (approximately 12 weeks total duration)
 

• Screening: Up to 21 days before randomization

• 8-week treatment period: 4 weeks of NYX-783 50 mg QD or 10 mg QD and 4 weeks of placebo or 8 weeks of placebo followed by a one-week post-therapy safety follow up period

○ Stage 1: 4 weeks

○ Stage 2: 4 weeks

Criteria for evaluation:

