12. Use of nefazodone, selective serotonin reuptake inhibitors (SSRIs, such as fluoxetine, sertraline, escitalopram, citalopram, paroxetine), serotonin and norepinephrine reuptake inhibitors (SNRIs, such as desvenlafaxine, duloxetine, venlafaxine), reversible and non-reversible monoamine oxidase inhibitors (such as selegiline, phenelzine, tranylcypromine), tricyclic antidepressants (such as amitriptyline, imipramine, nortriptyline), noradrenergic and specific serotonergic antidepressant (NaSSA) mirtazapine, serotonin modulator and stimulator antidepressants (such as vilazodone or vortioxetine), or the norepinephrine, serotonin and dopamine reuptake inhibitor bupropion within 30 days (90 days for fluoxetine) prior to screening or during the study. **NOTE:** Subjects on stable treatment ( $\geq 30$  days prior to screening) with St. John's Wort may continue this therapy during the study with no expected change in dose.
  13. Treatment with an injectable depot neuroleptic within 90 days prior to screening or during the study.
  14. Subjects who meet the criteria for suicidal intent, plan and/or behavior on the S-STS at screening or Day 1. These criteria are a score of 3 or 4 on questions 2 or 13, or 2 or higher on any of the following questions: 1a (only if 1b is coded YES), 3, 4, 5, 6, 7, 8, 9, 10, 11, 12, or 14.
  15. In the process of litigating for compensation for a psychiatric disorder. Subjects who are in the process of applying for medical or VA benefits and/or those who have settled a disability claim prior to enrollment in the trial are eligible.
  16. History of Huntington's, Parkinson's, and/or Alzheimer's disease, multiple sclerosis, seizures (history of childhood febrile seizures are not exclusionary), epilepsy, or stroke.
  17. History of allergy, sensitivity, or intolerance to N-methyl-D-aspartate receptor (NMDAR) ligands, including ketamine, dextromethorphan, memantine, methadone, dextropropoxyphene, or ketobemidone, as well as current use of such agents.
  18. Received an investigational drug product or device within 30 days (or 5 half-lives, whichever is longer for a drug product) of dosing.
  19. Previously received NYX-783.
  20. Screening QT interval corrected for heart rate (HR) by Fridericia's formula (QTcF)  $>450$  (males) or  $470$  (females) milliseconds (msec) or an ECG that is not suitable for QT measurements (e.g., poorly defined termination of T-wave in the investigator's opinion).

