## **13. STOPPING RULES AND SAFETY MONITORING**

### **13.1. Stopping Rules for Individual Subjects**

Any subject may withdraw consent at any point during the study. The investigator can discontinue a subject at any time if it is deemed medically appropriate, or for subject noncompliance with study requirements. Subjects will be withdrawn from the study if any of the following criteria are met:

- Occurrence of an AE, intercurrent illness, or laboratory abnormality which, in the opinion of the investigator, warrants the subject's permanent withdrawal from the study for subject safety
- Repeated results (i.e., values are confirmed by repeat testing as soon as feasible) showing any of one following laboratory findings:
  - Total bilirubin  $\geq 2.5$  mg/dL
  - ALT or AST  $> 3$  x ULN
  - ALT or AST  $\geq 3$  x ULN and total bilirubin  $\geq 2$  x ULN
  - ALT or AST  $\geq 3$  x ULN, with the appearance of fatigue, nausea, vomiting, right upper quadrant pain, or tenderness, fever, rash, or eosinophilia ( $> 5\%$ )
  - Alkaline phosphatase  $\geq 2$ x ULN
- 2 consecutive ECGs showing a new absolute corrected QT interval (QTc)  $\geq 500$  milliseconds (msec) that was not present on the corresponding baseline ECG, or a QT/QTc interval  $> 60$  msec over the corresponding baseline value. The QT interval should be corrected by Fridericia's (QTcF) formula.

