**Table 2 PCS criteria for lab tests**

Serum Chemistry	Alkaline Phosphatase (ALP)	> 2 x ULN
Serum Chemistry	Alanine Aminotransferase (ALT)	> 3 x ULN
Serum Chemistry	Aspartate Aminotransferase (AST)	> 3 x ULN
Serum Chemistry	Blood Urea Nitrogen (BUN)	> 1.5 x ULN
Serum Chemistry	Creatinine	>1.5 x Baseline or > 1.5 x ULN
Serum Chemistry	Gamma-Glutamyl Transferase (GGT)	> 3 x ULN
Serum Chemistry	Lactate Dehydrogenase (LDH)	> 3 x ULN

Serum Chemistry	Total Bilirubin	> 2 x ULN
Hematology	White Blood Cell Count	$\leq 2.8 \ 10^9/L$
Hematology	Absolute Neutrophils Count	$<1.5 \ 10^9/L$

Frequency distributions of the clinical laboratory tests of interest listed above will be summarized for PCS values at any post-baseline visit.

Evaluation of potential Drug-Induced Serious Hepatotoxicity (eDISH) will also be done by plot.

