## 9.6. Electrocardiograms

Descriptive summaries will be presented for ECG measures of PR interval, QRS interval, QT interval, QTc interval (both correction methods), and HR. These summaries will be presented by treatment group, Stage and visit.

The number and percentage of patients/subjects with normal and abnormal investigator reported ECG results will be summarized by visit and treatment group. An outlier analysis using QTcF will also be done based on these standard criteria. If the change from baseline QTcF values are > 30 or 60 msec, or if QTcF post baseline values are >450, 470 or 500. This will be done by Stage and Over All. Shift tables for results (normal, abnormal CS, abnormal NCS) from baseline to post-baseline visits will be presented by body system, treatment group, Stage and visit.

Bazett's correction (QTcb) and Fridericia's correction (QTcf) will be derived as follows:

Bazett's Correction (QTcb)	$QTc_b = \frac{QT_{msec}}{\sqrt{RR}}$
Fridericia's Correction (QTcf)	$QTc_f = \frac{QT_{msec}}{\sqrt[3]{RR}}$

Where: Relative Rate: RR = 60 / HR

HR = Heart Rate obtained from the ECG.

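### The SAP 9.6 QTcF outlier table does not separate values above a cut before dosing from new on-treatment values, although exclusion 20 lets women enter at 451–470 msec

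*Protocol*

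**What the plan says.** **Entry.** Exclusion 20, worded alike in the Protocol synopsis and in Protocol 8.2, sets the limits by sex: "Fridericia's formula (QTcF) $>450$ (males) or $470$ (females) milliseconds (msec"). It applies to the screening ECG: "20. Screening QT interval corrected for heart rate (HR) by Fridericia's formula (QTcF"). Another ECG is scheduled on Day 1, but no Day 1 QTcF limit is stated. SAP 6.1.1 takes the last value before the first dose as the Stage 1 baseline.

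**Reporting.** SAP 9.6 plans a QTcF outlier analysis with two kinds of criterion. One is relative: "If the change from baseline QTcF values are > 30 or 60 msec". The other is absolute and follows directly: "or if QTcF post baseline values are >450, 470 or 500". On level, the SAP adds: "This will be done by Stage and Over All". The same section plans "Shift tables for results (normal, abnormal CS, abnormal NCS) from baseline to post-baseline visits"; these use the investigator's overall reading of the ECG, not QTcF categories.

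**Design.** Under SAP 3.5, Stage 1 placebo subjects are re-randomised 3:2:2 to placebo, 50 mg or 10 mg for Stage 2, and subjects on active drug in Stage 1 move to placebo.

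**The concern.** A table of on-treatment QTcF outliers is read as showing what happened after dosing. As written, the absolute rows mix two groups: subjects who crossed a cut during treatment and subjects who were above it before any study drug. The relative and absolute criteria are joined by an *or*, so the change criterion does not qualify the absolute one.

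The two-stage design adds a complication. The same subject can contribute an unchanged value to more than one treatment column, because treatment is switched at Week 4 and the table is produced by Stage. With about 26 subjects per dose in Stage 1, one such subject is visible in the percentage.

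What is at stake is the clarity of a categorical safety display. A reader cannot tell from the >450 row how many cases are new.

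**Working it through.** The plan states no figure for this table, so there is none to reproduce. The check is a logical one, followed by an illustration of size.

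**1. The rule applied to an unchanged QTcF.** Change is zero, so only the absolute criterion can act. The new-onset rule counts a value above a cut only if baseline was at or below that cut.

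| QTcF at baseline and after (msec) | SAP 9.6 as written | New-onset rule |
|---|---|---|
| 445, 450 | not counted | not counted |
| 451, 455, 460, 465, 470 | counted in >450 | not counted |

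Every value in the band that exclusion 20 opens to women is counted. Because the entry limit applies at screening only, a man whose Day 1 value is above 450 would be counted in the same way.

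**2. How likely the count is when QTcF varies between visits.** With no drug effect, true value b and within-subject SD s, the chance that one later ECG exceeds 450 is 1 − Φ((450 − b)/s). The documents give no s, so 5, 10 and 15 msec are assumed.

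- b = 451: 58%, 54%, 53%
- b = 455: 84%, 69%, 63%
- b = 460: 98%, 84%, 75%
- b = 470: about 100%, 98%, 91%

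Such a subject is therefore likely, but not certain, to be counted.

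**3. Arm sizes.** 156 subjects at 4:1:1 give 104 on placebo and 26 on each dose in Stage 1. With the planned 15% Stage 1 dropout, 104 × 0.85 = 88.4 placebo subjects are re-randomised, and 88.4 × 2/7 = 25.3 go to each dose in Stage 2. The Stage 2 dose columns are thus about as small as those in Stage 1.

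**4. Expected number of pre-existing cases.** Assumptions: women's mean QTcF 412–425, between-subject SD 15–17, visit-to-visit SD 9–10, screening value at most 470, no drug effect, and 50%–70% women. Simulating screening, baseline and one post-baseline value gives, for women:

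| Assumed mean, between-subject SD, visit SD | Post-baseline >450 | Of which new (baseline ≤450) | Pre-existing |
|---|---|---|---|
| 412, 15, 9 | 1.45% | 1.00% | 0.45% |
| 425, 17, 10 | 9.4% | 5.0% | 4.4% |

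- Dose arm, low: 26 × 0.50 × 0.0045 = 0.06 subject. High: 26 × 0.70 × 0.044 = 0.80.
- Placebo arm, low: 104 × 0.50 × 0.0045 = 0.23. High: 104 × 0.70 × 0.044 = 3.2.
- As a share of the arm, low: 0.06/26 = 0.2% and 0.23/104 = 0.2%. High: 0.80/26 = 3.1% and 3.2/104 = 3.1%.

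The expected shares are equal across arms. Pre-existing cases make up 0.45/1.45 = 31% to 4.4/9.4 = 47% of all >450 counts among women.

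**The case against.** The strongest reply is that this changes little. The table is descriptive, randomisation spreads high baseline values across arms, and the >30 and >60 change rows stand beside the absolute rows. A woman unchanged at 460 appears in neither change row, and Protocol 14.10.3 lists all ECG data, so a flagged case can be checked. All of this is right, and it limits the point to a minor one. It does not give the reader a count of new cases, because the change rows are not tied to the absolute rows and the shift tables do not use QTcF.

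A second reply is that 450 and 470 may be meant for men and women respectively, as in exclusion 20. That would remove the case of women eligible at 451–470. The SAP does not say so, and the table shells are in a separate document.

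Several stronger readings are tempting and are not supported:

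- *The table is biased towards a drug signal.* One subject is 1/26 = 3.8 points in a dose column and 1/104 = 1.0 on placebo, but that holds for any event under 4:1:1 allocation. Expected percentages are equal.
- *All chance flags are pre-existing.* On the assumptions above there are about 0.2 to 1.7 flags among women per dose arm without a drug effect, but most of these (53%–69%) are new crossings from visit-to-visit variation.
- *The SAP dropped a condition the protocol sets.* The words "that was not present on the corresponding baseline ECG" belong to an individual withdrawal rule in Protocol 13.1. Protocol 14.10.3 plans only descriptive ECG statistics. The SAP added the outlier table and removed nothing.
- *The laboratory table has the same fault.* Values meeting the SAP Table 2 criteria "will be summarized for PCS values at any post-baseline visit", which also ignores baseline. But SAP 9.4 plans shift tables against baseline for each analyte. They use normal-range limits rather than the Table 2 cuts, so what remains is secondary.

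**Conclusion.** The point holds as a low-cost improvement to a safety display. SAP 9.6 as written counts subjects who were above a cut before dosing, and it can count one subject under placebo and then under NYX-783 with an unchanged QTcF. The textual part rests on no assumption.

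The size does. About 0.06 to 0.8 pre-existing case per 26-subject dose arm depends on an assumed QTcF mean, two assumed SDs and an assumed share of women, none of which the documents give. The calculation uses a single post-baseline ECG and covers women only. Within those limits the effect is non-differential noise. It inflates counts and blurs their meaning, without favouring either side of the comparison. No efficacy analysis, test or stopping decision rests on it.

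**What to change.** In SAP 9.6:

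1. Show each absolute cut (>450, >470, >500) as new-onset, meaning baseline at or below the same cut, or cross-tabulate post-baseline by baseline QTcF category.
2. State the baseline used in each Stage. SAP 6.1.1 takes the last value before Week 4 for re-randomised subjects, except groups [4] and [7], which keep the Stage 1 baseline. Before Week 8, treatment-period ECGs are scheduled only on Day 1 and at Week 4, so a literal reading gives the Day 1 ECG. If that is not intended, the SAP should say so. It should also name the baseline for groups [10] and [11].
3. Keep the all-subject counts and the >30 and >60 change rows.
4. State whether 450 and 470 are sex-specific. Making the rows sex-specific as well as new-onset is optional and can hide increases: a woman going from 425 to 454 (change 29) or from 455 to 469 (change 14) would appear in no absolute row and no change row.

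For the laboratory table, at most mark values that already met the Table 2 criterion at baseline.

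The cost is a few sentences, one programming condition, an extra row or column, and a slightly smaller denominator for the new-onset rows. No new data are needed. For this point, exclusion 20 and the Protocol 13.1 stopping rule need no change.
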